5.4 End of Study Definition and Premature Discontinuation

The end of the study is defined as the date of the last visit of the last participant in the study or last scheduled procedure shown in Table 5: Time and Events for the last participant in the trial globally.

The sponsor has the right to discontinue this study at any time. If the trial is prematurely terminated, the investigator is to promptly inform participants and will ensure they receive appropriate therapy, follow-up, and Exit Plan. If the study is prematurely discontinued, all procedures and requirements pertaining to retention and storage of documents will be observed. All other study materials will be returned to the sponsor and will be treated in accordance with federal and state regulations.

5.5 Rationale of Dose Selection

Similar MDMA doses to those proposed in this study have been safely used in previous Phase 2 studies sponsored by MAPS. Phase 2 studies indicate that 75, 100 and 125 mg MDMA initial doses with the supplemental dose are active and effective in two to three Experimental Sessions. MDMA doses with an optimal risk-benefit ratio range from 75 mg (Cohen's *d* Independent Groups Pre-test Post-test [d_{IGPP}]=2.73, N=7) to 125 mg (Cohen's d_{IGPP}=0.77, N=58) initial dose of MDMA with a 2-session treatment package. In Phase 2 studies, the sponsor observed a -36.4 point mean change in CAPS-4 scores among active dose participants receiving two Experimental

Sessions (N=72) compared to a -44.2 point mean change after three Experimental Sessions (N=51). Although uncontrolled, the additional 7.8 point mean reduction observed after three Experimental Sessions compared to two, along with the observed favorable safety profile formed the basis for selection of a 3-session treatment package. A flexible dosing regimen has been previously explored in Phase 2 studies, where participants who received doses of 0 mg to 75 mg MDMA in the blinded portion of the study crossed over to receive open-label 100 mg MDMA in the first Experimental Session with an option to increase to 125 mg MDMA in the second and third Experimental Sessions. In the opinion of the participants and therapy teams administering this treatment in Phase 2 studies, this flexible dosing regimen and three Experimental Sessions produced an optimal treatment response. Larger doses have been safely administered in MP2 (150 mg and 75 mg supplemental) and in Phase 1 studies (150 mg and 160 mg). The results of these Phase 2 studies led to the selection of 80 mg and 120 mg MDMA as the initial active doses.

This open-label study will examine the effects of a flexible dose of 80 mg to 120 mg MDMA administered in three Experimental Sessions. Initial doses per Experimental Session range from 80 mg to 120 mg MDMA compounded with lactose, followed 1.5 to 2 hours later by a supplemental half-dose (40 mg or 60 mg). A flexible dosing regimen was chosen to mimic proposed clinical practice and better adapt to risk-benefit considerations. The initial active doses of 80 mg and 120 mg are expected to produce all commonly reported effects of MDMA. The supplemental half-dose will prolong subjective effects of MDMA without producing physiological effects much greater than peak effects occurring after the initial dose and will be administered unless contraindicated. Total amounts of MDMA to be administered per Experimental Session range from 80 mg to 180 mg.

Table 3: Dose Regimen of MDMA

Experimental Session	Initial Dose	Supplemental Dose*	Min-Max Cumulative Dose
1	80 mg	40 mg	80 mg to 120 mg
2	80 or 120* mg	40 or 60 mg	80 mg to 180 mg
3	80 or 120* mg	40 or 60 mg	80 mg to 180 mg
	7	Total Cumulative Dose	240 mg to 480 mg

^{*} Unless contraindicated

In the first Experimental Session, the initial dose will be 80 mg MDMA. In the second and third Experimental Sessions, the initial dose may be increased to 120 mg MDMA unless contraindicated in the opinion of the site team. The choice of whether to keep the dose the same or change it from the first Experimental Session will be made by the site team based on observed response, tolerability to the previously administered dose, and discussion with the participant. In each Experimental Session, 1.5 to 2 hours after the initial dose is given, the participant will be administered a supplemental half-dose unless contraindicated.

6.0 Psychotherapy

6.1 Description of Therapeutic Method

The largely non-directive therapeutic method of MDMA-assisted psychotherapy is described in detail in the Treatment Manual. All therapy teams will be extensively trained in a multi-week training program prior to the study to ensure all participants are treated in a similar manner. The non-directive approach pertains to inviting inquiry and providing suggestion rather than directing the participant in the therapeutic approach. This requires active or engaged listening and responding, as well as facilitation of therapeutic action by providing support for approaching difficult material in a manner that does not interfere with the participant's spontaneous experience.

6.2 Therapy Team Qualifications

Therapy teams will be trained by the sponsor. Sites must ensure that the minimum requirements below are met:

- One person licensed to manage and administer controlled substances for each site
- A physician to assess participant safety at Screening
- One or more male/female therapy teams
- One person per therapy team is required to be licensed to provide psychotherapy according to state and local requirements
- If one person on the therapy team is unlicensed, they will work under the direct supervision of the licensed team member

6.3 Training

6.3.1 Therapy Training Program

The sponsor's Therapy Training Program is designed to teach competency in applying the essential elements of this method of MDMA-assisted psychotherapy. Therapy team members will receive specific training in the MDMA-assisted psychotherapy method, protocol, and latest version of the IB. Training in the psychotherapy method consists of reading the Treatment Manual, completing an online training module, and participating in an in-person training program that includes watching and discussing videos of Experimental Sessions. The required elements of the therapy are defined in the Treatment Manual, and teams will be trained on visit-specific sets of adherence criteria. In addition to this specific training, it is required that participating therapy team members have the proper background, education, and experience.

6.4 Adherence to Therapeutic Method

Psychotherapy sessions, including Experimental Sessions, may be recorded, with recordings preserved for research and training purposes. Adherence criteria and competence ratings will be conducted by qualified, trained, and adherence raters who will analyze video data from specific and randomly selected Preparatory Sessions, Experimental Sessions, and Integrative Sessions. The elements included in adherence criteria are specific to each type of session and are defined in the Treatment Manual. These ratings will be collected, at minimum, for each therapy team in the study. Ratings will be used to provide feedback to new therapy teams, to further characterize the manualized therapy, and for future exploratory research.

7.0 Measures and Reliability

The following eligibility, outcome, exploratory, and safety measures will be used in the study, in accordance with Table 6: Time and Events – Study Measures.

Table 4: Protocol Objectives and Assessment Tools

Objectives	Measure	Measure Type	Administration
Eligibility			
Assess Axis 1 psychiatric disorders	MINI	Eligibility	Site
Assess Axis 2 personality disorders	SCID-5-PD	Eligibility	Telemedicine
	with SCID-		(IR)/ self-report
	5-SPQ		measure at Site

Objectives	Measure	Measure Type	Administration
Confirm PTSD diagnosis and severity	PCL-5 with	Eligibility	Site
	LEC-5		
Identify dissociative disorders	DDIS	Eligibility	Site
Primary		T -	1
Assess changes in PTSD symptom severity	CAPS-5	Outcome	Telemedicine
from Visit 3 to Visit 19 compared between			(IR)
groups			
Secondary			
Assess changes in clinician-rated functional	SDS	Outcome	Telemedicine
impairment from Visit 3 to Visit 19			(IR)
compared between groups			
Safety			1
Compare relative incidence of positive or	C-SSRS	Safety	Site
serious ideation and suicidal behavior			
between groups			
Exploratory	GARS 5		m 1
Characterization of CAPS-5 Total Severity	CAPS-5	Outcome	Telemedicine
score at weeks 6, 10, and 18 to explore onset			
of treatment efficacy with a descriptive time			
course plot	CAPS-5	Outcome	Telemedicine
Explore changes in PTSD symptom clusters	CAPS-3	Outcome	Telemedicine
of re-experiencing, avoidance, negative			
alterations in cognition and mood, and hyperarousal as measured by changes in			
CAPS-5 subscale scores			
Assess overall changes in clinician-rated	SDS	Outcome	Site
functional impairment from Visit 3 to Visit	item scores	Outcome	Site
19 compared between groups	item scores		
Assess changes in severity of dissociative	DSP-I	Outcome	Site
symptoms associated with PTSD from Visit 3	-		
to Visit 19 compared between groups			
Explore correlation of dissociative symptoms	DSP-I	Outcome	Site
associated with PTSD with the CAPS-5 Total	CAPS-5		
Severity analyses			
Explore the effect of presence of secondary	LEC-5	Outcome	Site
traumatic stressors during the assessment	CAPS-5		
period as a covariate on the CAPS-5 Total			
Severity analyses			
Explore the effect of adverse childhood	ACE	Outcome	Site
experiences on PTSD treatment outcomes as	CAPS-5		
a covariate on the CAPS-5 Total Severity			
analyses	CARC 5	0.1	TD 1 1' '
Explore changes in PTSD symptom clusters	CAPS-5	Outcome	Telemedicine
of re-experiencing, avoidance, negative			
alterations in cognition and mood, and hyperarousal as measured by changes in			
CAPS-5 subscale scores			
Assess changes in depression symptoms from	BDI-II	Outcome	Site
Visit 4 to Visit 20 compared between groups	DDI II	Gutcome	510
Assess changes in chronic pain from Visit 4	CPGS	Outcome	Site
to Visit 20 compared between groups	0.00	3 3301110	2110
Assess changes in quality of life from Visit 4	EQ-5D-5L	Outcome	Site
to Visit 20 compared between groups	~		

Objectives	Measure	Measure Type	Administration
Assess changes in functioning in relation to	IASC	Outcome	Site
self and others from Baseline to Visit 20			
compared between groups			
Assess changes in self-reported psychosocial	IPF	Outcome	Site
functioning from Visit 4 to Visit 20			
compared between groups			
Assess changes in self-compassion from	SCS	Outcome	Site
Visit 4 to Visit 20 compared between groups			
Assess changes in alexithymia from Visit 4	TAS-20	Outcome	Site
to Visit 20 compared between groups			
Assess changes in alcohol use from	AUDIT	Healthcare cost	Site
Screening to Visit 20 compared between			
groups			
Assess changes in drug use from Screening	DUDIT	Healthcare cost	Site
to Visit 20 compared between groups			
Assess changes in nicotine use from Visit 4	SRNU	Healthcare cost	Site
to Visit 20 compared between groups			
Assess changes in disordered eating from	EAT-26	Healthcare cost	Site
Visit 4 to Visit 20 compared between groups			
Assess changes in workplace productivity	HPQSF	Healthcare cost	Site
from Visit 4 to Visit 20 compared between			
groups			
Assess facility-based healthcare utilization at	UFEC	Healthcare cost	Site
Screening			

7.1 Primary Outcome Measure and Reliability

CAPS-5 (Clinician-Administered PTSD Scale for DSM-5)

The last month CAPS-5 is a semi-structured interview that assesses index history of DSM-5defined traumatic event exposure [64], including the most distressing event, time since exposure, to produce a diagnostic score (presence vs. absence) and a PTSD Total Severity score [64]. The CAPS-5 rates intrusion symptoms (intrusive thoughts or memories), avoidance, cognitive and mood symptoms, arousal and reactivity symptoms, duration and degree of distress and dissociation. The CAPS-5 will be administered by a blinded IR via telemedicine. Interviews will be conducted by the centralized remote IR pool to enhance quality control by reducing site-level variation in interview fidelity and quality. The IRs will be trained and supervised by a research reliable trainer and will be supervised by qualified personnel. Per the CAPS-5 Training Manual for the IR Pool, IRs will ensure that every single item-level score is collected in every CAPS-5 interview. The CAPS-5 is administered by the IR in a neutral, non-leading manner to minimize the chance for bias. Avoiding a biased administration can be achieved by adhering to administration guidelines verbatim and only deviating from the script to clarify, re-direct, or query further if behavioral examples are needed to determine the appropriate symptom intensity rating. Avoiding building therapeutic/clinical rapport beyond the basic level of rapport needed to conduct the interview in the research setting also minimizes the chance for bias. Remote assessment assures that the rater who is collecting the Primary Outcome will not witness Experimental Sessions and the acute effects of IP. Interviews may be recorded in as many instances as necessary to establish reliability of a random selection of interviews for accuracy. After the initial screening visit, the IRs will be blinded to visit number, number of treatments received, and any study data for the participant. IR visits will be assigned based on availability.

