ent	Baseline CAPS-5 T1 (Visit 3)	1.5 hours/ Post V2 & Medication Taper; before V4	CAPS-5, SDS, and DSP-I completed by an IR via telemedicine after taper is complete. CAPS scores sent ASAP to the therapy team/PI.	
Baseline & Enrollment Confirmation	Preparatory Session 3 & Enrollment Confirmation (Visit 4)	3 hours: (95 minutes of measures, 90 minute therapy) Within 6 days of V3	Prior to visit, ensure CAPS-5 confirms PTSD diagnosis and Total Severity Score of ≥35 and confirm enrollment by reassessing specified eligibility criteria. Complete Baseline self-report measures. Complete 3 hour Preparatory Session (~95-min measures, 90-min therapy) and schedule V5. If enrollment is not confirmed, do not perform visit; complete termination and put on waiting list for Expanded Access study if appropriate.	

Treatment Period From Experimental Session 1 (Visit 5) to Integrative Session 3.3 (Visit 18): 12 weeks (-3/+4)			
Study Visit/ Visit #		Visit Duration/ Visit Timing/ (Scheduling Window)	Brief Description of Events
	Experimental Session 1 (Visit 5)	8 hours + overnight/ Within 1 week of V3, at least 2 weeks after V2	First Experimental Session is within 1 week of the Baseline CAPS-5 (V3) and 2 weeks after Preparatory Session 2 (V2); it lasts 8 hours with overnight stay. Dose is 80 mg with supplemental half-dose of 40 mg unless contraindicated.
ıt 1	Integrative Session 1.1 (Visit 6)	1.5 hours/ Morning after V5	V6 is a 90-minute Integrative Session the morning after V5. Followed by 4 phone check-ins over the 7 days post V5.
Treatment 1	Integrative Session 1.2 (Visit 7)	1.5 hours/ within 2 weeks of V5	Approximately 2 weeks after V5, a 90-minute Integrative Session (V7) is completed.
	CAPS-5 T2 (Visit 8)	1 hour Within 3 weeks after V5 Complete before V9	Between V7 and V9, CAPS-5, SDS, and DSP-I assessment completed by an IR via telemedicine.
	Integrative Session 1.3 (Visit 9)	1.5 hours/ Within 4 weeks of V5 1-7 days before V10	90-minute Integrative Session post V8 and in preparation for V10. Can occur 1 to 7 days before V10. Measures include LEC-5, PCL-5, and C-SSRS.

Study Visit/ Visit #		Visit Duration/ Visit Timing/ (Scheduling Window)	Brief Description of Events

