8.3.3 Integrative Sessions

After each Experimental Session, three Integrative Sessions will take place. Each session will consist of 90 minutes of psychotherapy.

Treatment 1

- Integrative Session 1.1 (Visit 6): morning after Experimental Session 1 (Visit 5)
- Integrative Session 1.2 (Visit 7): approximately 2 weeks after Experimental Session 1 (Visit 5)
- Integrative Session 1.3 (Visit 9): within 3 to 5 weeks of Experimental Session 1 (Visit 5) and 1 to 7 days in advance of Experimental Session 2 (Visit 10). This visit serves two purposes: to continue integration and to prepare for the next Experimental Session. The participant will complete the LEC-5 and PCL-5 self-report measures.

Treatment 2

- Integrative Session 2.1 (Visit 11): morning after Experimental Session 2 (Visit 10)
- Integrative Session 2.2 (Visit 12): approximately 2 weeks after Experimental Session 2 (Visit 10)
- Integrative Session 2.3 (Visit 14): within 3 to 5 weeks of Experimental Session 2 (Visit 10) and 1 to 7 days in advance of Experimental Session 3 (Visit 15). This visit serves two purposes: to continue integration and to prepare for the next Experimental Session. The participant will complete the LEC-5 and PCL-5 self-report measures.

Treatment 3

- Integrative Session 3.1 (Visit 16): morning after Experimental Session 3 (Visit 15)
- Integrative Session 3.2 (Visit 17): approximately 2 weeks after Experimental Session 3 (Visit 15)
- Integrative Session 3.3 (Visit 18): within 3 to 5 weeks after Experimental Session 3 (Visit 15). This visit will be the final Integrative Session prior to entering the follow-up period. The participant will complete the LEC-5 self-report measure.

During Integrative Sessions, the therapy team will:

- Record the session.
- Inquire about any possible changes in health. Assess the participant's mental health and the status of any previously recorded AEs. Record AEs as described in Section 11.0 Safety.
- Inquire about concomitant medication use and adherence.
- Administer Since Last Visit C-SSRS to determine suicidal risk.

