8.3.4 Independent Rater Assessments

Participants will have two CAPS-5 assessments during the treatment period of the study (Visits 8 and 13). An IR from the IR Pool will conduct the assessments via telemedicine. These assessments may be recorded to establish inter-rater reliability. The results may be shared with site staff, but the IR Coordinator will enter the data. The IR will also administer the DSP-I and SDS at these time-points:

- CAPS-5 T2 (Visit 8): 3 weeks after Experimental Session 1 (Visit 5), between Integrative Session 1.2 (Visit 7) and Integrative Session 1.3 (Visit 9)
- CAPS-5 T3 (Visit 13): 3 weeks after Experimental Session 2 (Visit 10), between Integrative Session 2.2 (Visit 12) and Integrative Session 2.3 (Visit 14)

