# 8.7.4 Responder Analyses

The CAPS-5 produces a Total Severity Score based on severity of PTSD symptom domains described in the DSM-5, as well as a categorical rating indicating whether a participant meets PTSD diagnostic criteria. A psychometric validation study found the following severity score ranges for the CAPS-5: Asymptomatic (0-10), Mild (11-22), Moderate (23-34), Severe (35-46), Extreme (47+). Based on these data, a 10-point reduction in CAPS-5 Total Severity Score is clinically meaningful. As an alternate definition of treatment response to assess clinical significance of study outcomes, the sponsor will conduct a responder analysis to support findings from the primary effectiveness analysis, and to explore how many single-dose treatments are needed to achieve response (See Figure 1).

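### At T2 and T3 the last-month CAPS-5 partly rates time before the latest session, so the exploratory responder analysis cannot show how many treatments are needed

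*Protocol*

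**What the plan says.** **Recall period.** Protocol Section 7.1 opens its description of the primary scale with "The last month CAPS-5 is a semi-structured interview". No shorter version is named for T2 or T3. The C-SSRS, by contrast, has a separate version covering the time since the last visit (Section 7.3).

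**Timing.** Section 8.3.4 puts T2 (Visit 8) 3 weeks after Session 1, between Visits 7 and 9, and puts T3 (Visit 13) in the same position after Session 2. The synopsis visit table gives the T2 window as "Within 3 weeks after V5 Complete before V9", and Visit 13 has a matching rule. The lower end comes from Section 8.3.3: "Integrative Session 1.2 (Visit 7): approximately 2 weeks after Experimental Session 1", with Visit 12 placed likewise after Session 2. T4 (Visit 19) is 8 weeks, plus or minus 2, after Session 3 (Section 8.4.2).

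**Use.** Protocol Table 4 lists the CAPS-5 "score at weeks 6, 10, and 18 to explore onset" of efficacy in a descriptive plot, and SAP Section 8.7 plots the scores across visits for the same purpose. SAP Section 8.7.4 plans a responder analysis, in part "to explore how many single-dose treatments are needed to achieve response". The footnote to SAP Figure 1 compares T2, T3 and T4 each with T1. Protocol Section 5.1 calls the T2 and T3 assessments exploratory.

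**The concern.** The three post-baseline assessments do not measure the same thing. The month rated at T4 lies wholly after Session 3. The months rated at T2 and T3 reach back before the session whose effect they are meant to show. Raters are blinded to visit number and number of treatments and are told to follow the administration guidelines verbatim (Sections 7.1 and 9.4), and neither document tells them to confine ratings to post-session days.

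If sessions reduce symptoms, this overlap tends to hide part of the early change and show it at the next assessment. Taken at face value, the responder analysis would then lean towards more sessions being required. SAP Section 9.0 says preliminary analyses will inform Phase 3 assumptions, so a statement about how many treatments are needed could be carried forward although the schedule cannot support it.

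**Working it through.** **1. The plan's own timing labels.** Protocol Table 2 gives target times after Baseline (V3) of about 6 weeks (T2), 10 weeks (T3) and 18 weeks (T4). Inputs: Session 1 within 1 week of V3 (Section 8.3.1), sessions 3 to 5 weeks apart (Section 8.3), T2 and T3 up to 3 weeks after Sessions 1 and 2, T4 8 weeks after Session 3.

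- T2 = 1 + 3 = week 4 at the latest, not about 6.
- T3 = 1 + 4 + 3 = week 8 at 4-week spacing, or 1 + 5 + 3 = week 9 at 5-week spacing, not about 10.
- T4 = 1 + 4 + 4 + 8 = week 17, which fits about 18.

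The T2 and T3 labels are not reproduced. At 4-week spacing Session 2 falls at week 1 + 4 = 5, so a week-6 T2 would come after the session it must precede.

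**2. Share of the rated month before the latest session.** Let M be the length of the month in days and d the days from the session to the interview. Share = max(0, M − d)/M. The documents give no day count for the month, so M = 28 and M = 30 are both shown as an assumption.

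| Days after session | M = 28 | M = 30 |
|---|---|---|
| 14 (just after Visit 7 or 12) | 14/28 = 50% | 16/30 = 53% |
| 21 (target) | 7/28 = 25% | 9/30 = 30% |
| 42 to 70 (T4) | 0% | 0% |

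The visit tables also word Visits 7 and 12 as within 2 weeks, so an earlier interview is not excluded there. At day 7 the share would be 21/28 = 75% or 23/30 = 77%.

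**3. What the pre-session days contain.**

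- At T2 they precede any study drug, and some may already have been rated at Baseline. With V3 falling g = 1 to 7 days before Session 1, the shared days are max(0, M − d − g): from 28 − 21 − 7 = 0 to 30 − 14 − 1 = 15.
- At T3 the most that can predate Session 2 is 30 − 14 = 16 days. Sessions are at least 21 days apart, so all 16 fall after Session 1.

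**4. Other differences between the assessments.** The lag is 2 to 3 weeks at T2 and T3 and 6 to 10 weeks at T4. All participants are scheduled for three sessions whatever their response. A first response at T3 or T4 may therefore be a delayed or newly fully rated effect of an earlier session, or an effect of the later one. No planned comparison separates these.

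**The case against.** The strongest reply is that T2 and T3 are exploratory, the onset plot is descriptive, the SAP says only that it will explore the question, and the V19 assessment has no overlap. That stands, and it makes this a limit on interpretation, not a fault in the primary endpoint. T2 and T3 scores do enter the repeated-measures model, so its estimates at those visits carry the same recall period.

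It is also fair that SAP Figure 1 is not visible beyond its title and footnote and may already display cumulative response. The stated purpose in the text would still need changing.

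A reader might infer more than the documents support:

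- **A size in points.** If the effect were immediate and the score a simple average over the month, a true 10-point fall (the reduction SAP 8.7.4 treats as clinically meaningful) would read at T2 as 10 × 14/30 = 4.7 to 10 × 21/28 = 7.5 points. Neither document says how a month with changing symptoms is scored. Weight on recent weeks would shrink the effect, and weight on the worst period would enlarge it.
- **T2 and T3 response rates as lower bounds.** Entry requires a score of at least 35 on the same V3 assessment that serves as Baseline, and treatment is open-label. Regression to the mean and expectancy can raise response rates, so the net direction is not known.
- **The Phase 3 three-session choice rests on this analysis.** Protocol Section 5.5 bases that choice on earlier Phase 2 data: mean changes of −36.4 after two sessions and −44.2 after three, a difference of 7.8 that it describes as uncontrolled.
- **Interviewing just before Visits 9 and 14 would cure it.** Visit 9 may fall 1 to 7 days before Session 2. With Session 2 at day 28 and Visit 9 at day 21, Visit 8 lands at about day 20, leaving 10/30 = 33%, no better than the present target.

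**Conclusion.** The point holds as a limit on the exploratory analyses. With a month of 28 to 30 days, 25-30% of the rated period at the 3-week target, and 50-53% at day 14, predates the latest session, against none at T4. The overlap follows from the visit windows. Its effect on scores is conditional: if sessions reduce symptoms, it tends to understate early change and shift apparent response to later assessments, by an amount the documents do not allow anyone to calculate. At T3 only the added effect of Session 2 is diluted. Together with the unequal lags and the fixed three-session schedule, this means SAP Section 8.7.4 can describe response by each assessment but cannot say how many treatments are needed. Separately, the week-6 and week-10 labels contradict the protocol's own windows.

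**What to change.** 1. In SAP Section 8.7.4, replace the purpose "to explore how many single-dose treatments are needed to achieve response" with *to describe cumulative response observed by T2, T3 and T4*.
2. Add there that the recall month at T2 and T3 includes days before the latest session, and that non-response at T2 or T3 is not evidence that a further session was needed.
3. Tabulate days from the last session to each CAPS-5, and show that interval with the onset plot and the response rates.
4. Reconcile the week-6 and week-10 labels (Protocol synopsis, Table 2 and Table 4) with the 3-week windows (synopsis visit tables, Table 1, Table 5, Section 8.3.4 and SAP Table 2).

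Items 1 to 3 need only SAP wording and a derived interval from dates of scheduled visits; no visit or treatment changes. Item 4 is a consistency correction in both documents. The downside is a weaker exploratory claim about number of sessions.
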